Study 2 Randomized Pilot Trial: Up to 96 participants will be enrolled into the trial. The pilot trial was not powered for hypothesis testing, as the goal of the pilot is to inform a R01 trial of an optimized intervention. This goal will be achieved by evaluating feasibility and generating effect sizes of each component on changes in outcomes.³⁹⁻⁴¹ The effect sizes will inform which components to retain in the optimized intervention and be used to power a subsequent trial. However, a power calculation was run to determine the effect size this pilot trial will be powered to detect. Using intent-to-treat analyses with $n=36/\text{group}$ for tests of each component (Aim 2b), assuming 80% power, 5%

alpha, and a two-sided test, there is power to detect main effects of $d=0.67$. This effect is in the range of past trials of digital BWL and CBT.^{26-29,42-47} It is acknowledged that this is a large effect; however, because the primary purpose of this research is for training and to collect pilot data, increasing the sample size could decrease feasibility and threaten these two goals. As such, a smaller N to maintain appropriate scope was prioritized.

4.0 Recruitment and Screening Methods:

Recruitment Methods, Study 1 Needs Assessment: Participants will be recruited from potentially eligible individuals who have consented on discord to complete screens and be considered for qualitative research projects (i.e., “missions”).

Recruitment Methods, Study 1 Design & Usability Testing (including the Field Trial) and Study 2 Randomized Pilot Trial: Participants will be recruited from clinics at Northwestern University (e.g., Center for Lifestyle Medicine) and the University of Chicago (e.g., Eating Disorders Program, Center for Surgical Treatment of Obesity) and the community via flyers, media (including online social media such as Facebook, Instagram, Reddit, and Craigslist), newsletters, referrals, and word of mouth. We also will recruit participants using ResearchMatch and The New Normal, which are free participant recruitment online platforms that are accessible to researchers at participating institutions including Northwestern University, and Northwestern’s StudyTracker. Across all recruitment method platforms, information/study advertising content will remain consistent with IRB-approved recruitment language.

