### Statistical Analysis Plan

Data will be stored in the Research Electronic Data Capture (REDCap) program on a HIPAA-compliant server with secure access for approved study staff. Analyses will be conducted using SPSS and Supermix. For Aim 2a, I will calculate averages of acceptability ratings, number of sessions completed (retention to treatment), and prescribed strategies documented (compliance). These data will be used to derive expected usage rates for a future trial. For Aim 2b, I will assess the effect of each component on changes in weight and binge eating across time (baseline, post-intervention, follow-up), which will be done by comparing combinations of participants across conditions (see C.5 Research Design). Analyses will be conducted using intent-to-treat linear (for weight) or Poisson (for binge eating) mixed effects models, accounting for data collected at multiple assessment time points nested within individual participants. For each component, I will test differences in change in outcomes across time, with baseline values as the reference. Thus, effects will be modeled as component x time interactions. Cohen's d will be calculated by dividing the mixed effects model derived intervention effect estimate by the pooled standard deviation of the outcome. I also will report results disaggregated by sex and test sex as a moderator to evaluate sex differences in outcomes, which will inform the need for any sex-specific approaches in an optimized intervention. For Aim 3, exploratory analyses using linear mixed models will be performed to test two-way interactions between components on changes in weight and binge eating (e.g., Component 1 x Component 2 x time). Interaction tests are to determine if a set of components impact the overall effect and thus should be retained together in the optimized intervention.

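### The SAP's single rule for Cohen's d gives no interpretable effect size for binge eating, and for weight matches a two-group d for change only if the baseline correlation is 0.5

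*Protocol*

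**What the plan says.** Protocol section 3.0 (Sample Size, Study 2) states that the pilot was not sized for hypothesis tests, but that "a power calculation was run to determine the effect size this pilot trial will be powered to detect". The inputs are given as "Using intent-to-treat analyses with $n=36/\text{group}$ for tests of each component", with 80% power and a two-sided 5% level, and the result as "there is power to detect main effects of $d=0.67". No test, outcome, standardising SD, baseline correlation, binge-eating rate or between-person variance is named. The same section says that the effect sizes from the pilot will guide the choice of components and the sample size of the next trial. Aim 2 in section 1.0 also ties the estimates to that next trial.

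The SAP (Aim 2b) uses a linear mixed model for weight and a Poisson mixed model for binge eating, with baseline as the reference time. "Thus, effects will be modeled as component x time interactions". One rule then covers standardisation: "Cohen's d will be calculated by dividing the mixed effects model derived intervention effect estimate by the pooled standard deviation of the outcome". It is not limited to weight, and nothing is said about transforming the Poisson estimate.

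**The concern.** The main product of this pilot is a set of effect sizes, so how they are standardised matters more than any p-value. The SAP applies one formula to two models whose estimates are on different scales.

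- **Binge eating.** A Poisson model's component-by-time coefficient is the log of a ratio of rate ratios. The SD of the outcome is in episodes. The quotient is not a standardised mean difference.
- **Weight.** The coefficient is a difference in change, in kg. Read plainly, the rule divides it by the SD of weight, not by the SD of change in weight. A two-group sample-size formula applied to change needs the latter.

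If these values were carried into the next trial without their denominators, a useful component could look negligible, or the trial could be sized on the wrong scale. The d=0.67 in section 3.0 does not help the reader, because it does not say which outcome or SD it refers to.

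**Working it through.** **Inputs from the documents.** 36 per group, 80% power, two-sided 5% and d=0.67 (protocol 3.0). Binge episodes are counted over 28 days (protocol 8.0). The models, the component-by-time target and the definition of d come from the SAP. **Assumed, because the documents give no values:** the correlation r, the kg and SD values in step 4, and the binge-eating rates and between-person variance in step 5.

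**1. The plan's own figure.** A two-sample t-test (noncentral t, 70 df, two-sided 5%) with 36 per group detects d=0.6696 at 80% power; power at d=0.67 is 80.05%. The normal approximation gives (1.960+0.842)×√(2/36)=0.660. So 0.67 reproduces. The calculation has no term for repeated measures or counts.

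**2. Binge eating.** Let b be the Poisson component-by-time estimate (log scale) and s the SD in episodes per 28 days. The SAP's d is b/s. Now express the same data as episodes per week (28/7=4). The ratio of rates, and so b, is unchanged, but the SD becomes s/4 and d becomes 4b/s. A genuine standardised effect does not quadruple when the time unit changes.

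**3. Weight.** With equal SDs at both times, SD of change = SD of weight × √(2(1−r)). A contrast detectable at 0.6696 SDs of change is therefore detectable at 0.6696×√(2(1−r)) SDs of weight:

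| r (assumed) | √(2(1−r)) | Detectable SAP-scale d, 36 per group |
|---|---|---|
| 0.3 | 1.183 | 0.79 |
| 0.5 | 1.000 | 0.67 |
| 0.9 | 0.447 | 0.30 |
| 0.95 | 0.316 | 0.21 |

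The two scales agree only at r=0.5. Above that, the SAP's d is smaller than the d for change; below it, larger.

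**4. What that could do to a later sample size (illustration, all values assumed).** Take a 2 kg difference, SD of weight 20 kg and SD of change 5 kg, so r=1−25/(2×400)=0.97. The SAP's d is 2/20=0.10; per SD of change it is 2/5=0.40. With n per group = 2×(2.80/d)², the first gives about 1,570 and the second about 98, for one and the same result.

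**5. What a sensitivity figure for binge eating would need.** As an approximation, the variance of change in log rate is v=1/μ0+1/μ1+τ², where μ0 and μ1 are the mean counts before and after and τ² is the between-person variance in change. The detectable log ratio is 2.80×√(2v/36). With means falling from 16 to 8 and τ²=0, v=0.1875, the log ratio is 0.286 and the detectable ratio of rate ratios is 0.75. With means falling from 4 to 2 and τ²=1, v=1.75, the log ratio is 0.874 and the ratio is 0.42. The answer depends on quantities the documents do not give, and d=0.67 cannot be converted to it without them.

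**The case against.** A reader might infer that the power statement is wrong for both outcomes, or that 0.67 describes the sensitivity of neither analysis. The documents do not support that. The figure is arithmetically correct. Section 3.0 leaves its SD undefined and speaks of component effects on changes in outcomes. If d is per SD of change, 0.67 is a fair figure for one baseline-to-post weight contrast at 36 per group. If it is per SD of weight, it shares the SAP's denominator and is conservative whenever r exceeds 0.5. The SAP's outcome SD could even be read as the SD of change, although that is the less natural reading; the two scales would then agree for weight.

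A reader might also infer that the SAP's d will be judged against 0.67. Neither document says so. They say only that the effect sizes will guide component selection and power the next trial, and they give no formula. The 1,570-versus-98 contrast further requires an analyst who ignores the SD of change that the trial's own data will supply. The protocol also disclaims formal power, and no decision rule rests on 0.67.

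These points limit the consequence for weight and clear the 0.67 of error. They do not rescue the rule for binge eating. The analyst might intend to convert the Poisson estimate to a difference in episodes before dividing, but the SAP does not say so, and as written the rule divides a log ratio by a count SD.

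**Conclusion.** The point holds as a fault in the SAP's standardisation rule and as an incomplete power statement. For binge eating the rule yields an uninterpretable number under any reading of section 3.0; this needs no assumption beyond taking the SAP's formula as written. For weight the rule yields a legitimate quantity, but one that differs from a two-group d for change by the factor √(2(1−r)). That conclusion rests on the plain reading of outcome SD, on equal SDs at the two times, and on a single baseline-to-later contrast with complete data. That r for weight is high is a reasonable expectation, not something the documents state. The ranges in steps 3 to 5 show dependence on unknowns and are not estimates for this trial.

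The effect on this trial's own inference is small. The effect on its stated use, choosing components and sizing the next trial, could be large, so the rule should be corrected before the effect sizes are produced.

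Separately, "Up to 96 participants will be enrolled into the trial" implies 96/2=48 per component level under equal allocation, not 36; the same t-test then gives 0.578. No dropout rate is stated to explain the gap. That should be reconciled but is not part of this point.

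**What to change.** **SAP, Aim 2b.** Replace the single rule with two:

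- For binge eating, report the component-by-time effect as a rate ratio (a ratio of rate ratios over time) with its confidence interval, in place of Cohen's d.
- For weight, report the effect in kg with its confidence interval, the SD of change and the baseline-to-follow-up correlation. Standardise by the SD of change whenever the value is to enter a two-group sample-size formula.

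**Protocol 3.0.** State that 0.67 is per SD of change and applies to weight only. Add a rate-ratio sensitivity for binge eating under the planned Poisson mixed model, with event rates and between-person variance labelled as assumptions and shown over a range.

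**Cost.** A few sentences across the two documents and a less simple power statement. No change to the design, the models or the number of participants.

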Potentially-eligible individuals will be invited to complete a baseline assessment. First, participants will complete informed consent. Consenting individuals then will complete the baseline assessment, which will include a semi-structured interview with a trained assessor, followed by questionnaires administered via REDCap to confirm eligibility. Following the session, participants will be emailed their eligibility status. Ineligible individuals will be notified via e-mail that they are ineligible and offered referral information for treatment. Eligible individuals will be notified via e-mail that they are eligible and will be invited to enroll in the pilot trial. Enrolled participants will be randomly assigned to 1 of 8 experimental conditions; randomization will be performed using a computerized random-number generator to assign participants to an experimental condition with an 8:1 ratio. Enrolled participants

will then be contacted by a member of the research team to schedule a call with their Coach to begin the intervention. The call will occur by telephone or an internet-based phone service (e.g., Google Hangouts/Voice, CiscoJabber, Zoom).

Intervention: Participants will be offered access to the mobile intervention, FoodSteps, with coaching for 16 weeks. Participants can continue using the intervention after the 16 weeks of coaching ends. The intervention is focused on addressing binge eating and weight management, with recommended weekly modules for participants to complete. Participants will access the intervention by creating a personal password known only to the participant. FoodSteps can be accessed as an app on a smartphone or as a website on a smartphone or computer. Participants can use or not use the intervention and still be enrolled in the study. The intervention and data are hosted on a secure, encrypted server. The information that participants enter into the app will not include anything that can identify them except for their email address, phone number, and zip code, and will not include the information they provide in the study assessments.

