Coaching: Each participant will be assigned a coach, trained and supervised weekly by a licensed clinical psychologist. Coaching follows a low-intensity model aimed at encouraging participants to use the intervention and practice skills in their daily lives, as well as provide some technical support as needed. Coaches will use messaging such as text or e-mail to communicate with participants through a password-protected website on a secure server. Coaching will begin with an initial ~30-minute phone call to establish goals and build rapport, ensure the participant can access the intervention, and set expectations for the coach-participant relationship. Thereafter, participants will receive ~1-2 messages per week from their coach to offer encouragement, reinforce app use, and check-in on progress or challenges. Coaches also will aim to respond to participant-initiated messages within 1 working business day. An optional ~10-minute call at week 8 (mid-way through the intervention) will be offered to participants to check in on their progress.

Study assessments will occur at the following intervals: baseline, mid-intervention (5-weeks and 10-weeks), post-intervention (16 weeks) and follow-up (3-months post-intervention). Baseline, post-intervention, and follow-up assessments will include interviews and questionnaires; mid-treatment assessments will only include questionnaires. Interviews and questionnaires will assess the following topics: personal and demographic information, treatment utilization, height, weight, number of binge episodes over the past 28 days, eating-related, cognitions, behaviors, and impairment, food security, eating and physical activity behaviors, social support for diet and exercise, mood, and experiences with technology. Intervention use data (from start of

intervention through 3-month follow-up) also will be automatically collected. Study procedures will be conducted remotely during remote work requirements. Upon return to work, participants and researchers will have the option conduct these activities remotely or in-person.

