For in-person procedures, interviews and questionnaires will be conducted in a private room at CBITs. Height and weight will be measured by an approved research member. Procedures for in-person height/weight measurements include up to three measurements if needed to resolve any measurement discrepancies, and the average will be used. For remote procedures, interviews will be conducted using Zoom video call and questionnaires will be e-mailed as a REDCap link to participants after the call ends. For remote procedures, height and weight will be self-reported as a part of the questionnaires; participants also will be asked to upload a photo of their weight on a scale to verify their weight. If needed (e.g., due to social distancing guidelines), participants will be presented the option to participate in assessments remotely if they started the baseline in-person, and vice versa.

As noted, questionnaires will be delivered via REDCap survey and interviews will be administered by a trained assessor. Participants can choose not to answer any questions as a part of the interviews or questionnaires and can stop the assessments at any time. To improve reading comprehension in the questionnaires, “helper text” may be added in REDCap to questions that appear challenging to understand. As Study 2 is a clinical trial, the study will be registered in Clinicaltrials.gov within 21 days of the first enrolled participant beginning the study.

Intervention use data will be downloaded monthly from the intervention and in entirety at the end of the study by an approved member of the research team. Following the study, all intervention use data will be removed from the intervention host server. All data will be stored in FSM research files on password protected computers on secure servers, or the Research Electronic Data Capture program on a HIPAA-compliant server with secure access for approved study staff.

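### Randomising before the starting coach call is scheduled lets people who never begin their assigned components into the intent-to-treat effect sizes; drawing the assignment at the call would avoid this

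*Protocol*

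**What the plan says.** Protocol section 8.0 (Study 2 Randomized Pilot Trial) gives this order: consent, baseline interview and questionnaires, eligibility e-mail, invitation to enrol, randomisation, contact to arrange the coach call, then the call itself. On assignment it says "Enrolled participants will be randomly assigned to 1 of 8 experimental conditions". Of the same people it then says that they "will then be contacted by a member of the research team to schedule a call with their Coach to begin the intervention". No limit is placed on the time between the two steps.

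The Intervention paragraph of the same section allows a participant to stay enrolled without using the app. The SAP analyses weight and binge eating with intent-to-treat mixed models, and computes Cohen's d from the model's estimate of the intervention effect. Section 3.0 says the resulting effect sizes will decide which components to keep and will power a later trial.

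Assessments are listed as "baseline, mid-intervention (5-weeks and 10-weeks), post-intervention (16 weeks) and follow-up (3-months post-intervention"). The event from which the weeks are counted is not named, and no visit windows are given.

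**The concern.** A person who drops out of contact after randomisation but before the call has, as the plan describes the start, not begun any assigned content. Participants are also masked to condition, so the loss says little or nothing about any component. It still counts in the randomised set. Depending on whether the person returns for outcome visits, it either pulls the component contrast toward zero or reduces the information available.

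This matters more than usual in a pilot whose main product is a set of effect sizes. A component judged too weak to keep, or a next trial sized on a shrunken d, could reflect scheduling losses rather than the component.

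**Working it through.** **Inputs from the documents.** Section 3.0: 36 per group for each component test, two-sided 5% alpha, 80% power, detectable d = 0.67, enrolment of up to 96. Under equal allocation (assumed), 96 gives 96/2 = 48 per component level, whereas 36 per group is 72 in total. The protocol does not explain that step, so both group sizes are shown.

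**Input not in the documents.** The never-start rate p. The values 5, 10 and 15% are assumptions.

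**Step 1: the plan's own figure.** For a two-sample comparison with SD = 1, the normal approximation gives d = (1.960 + 0.842) × √(2/36) = 0.660. The t-test gives 0.670, with 80.1% power at d = 0.67. The protocol's figure is reproduced.

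**Step 2: never-starters who return outcome data.** Let δ be the component effect among starters. If a share p at each level of the component never starts and gets no component effect, the expected difference is (1 − p) × δ + p × 0 = (1 − p)δ. This assumes that p is the same in all conditions, that the SD is unchanged and that never-starters all supply outcomes. The sample needed for the same power rises by 1/(1 − p)².

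| p (assumed) | d = 0.67 × (1 − p) | Power, 36/group | Power, 48/group | Sample inflation |
|---|---|---|---|---|
| 0% | 0.67 | 80% | 90% | 1.00 |
| 5% | 0.64 | 76% | 87% | 1.11 |
| 10% | 0.60 | 71% | 83% | 1.23 |
| 15% | 0.57 | 66% | 79% | 1.38 |

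**Step 3: never-starters with no post-baseline data.** They add almost nothing to a component-by-time estimate, so the expected effect is not shrunk. If they come out of the 36, the group falls to 36 × (1 − p) = 34.2, 32.4 or 30.6. The detectable d rises by about 1/√(1 − p), to 0.67 × 1.026 = 0.69, 0.67 × 1.054 = 0.71 or 0.67 × 1.085 = 0.73. This is the milder cost. A real trial would probably see a mixture of the two cases.

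**Step 4: the assessment clock.** Three places bear on it.
- Section 1.0 equates 16 weeks with the end of the intervention.
- The assessment list in section 8.0 labels weeks 5 and 10 as falling within the intervention and week 16 as after it.
- The Coaching paragraph treats week 8 as the halfway point.

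All three fit a count from the start of the intervention, which puts week 16 at 16 of 16 weeks whatever the scheduling delay. A count from randomisation with, say, a 3-week delay would give 16 − 3 = 13 weeks, but both the delay and that clock would be assumptions, and the clock conflicts with the labels.

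**The case against.** The strongest reply is that keeping non-users is deliberate. The protocol allows non-use, the analysis is intent-to-treat, and retention to treatment is itself a feasibility outcome. If the next trial also randomises at enrolment, an effect that includes never-starters is the right planning value, and a starters-only effect would be optimistic. This stands as an argument for reporting the pre-start loss, and the proposed change does report it. It is weaker as an argument for blending the loss into d: kept separate, the two figures can be recombined for whatever design follows, and everyone randomised is still analysed.

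Three further limits stand. First, no never-start rate is documented, so the size of the dilution is conditional. Second, dilution and missing data are alternatives for any one person; the factor (1 − p) applies only to those who come back for outcomes. Third, it is an inference that the condition is not needed before the call. Section 8.0 says only that the call makes sure the participant can get into the app, which would also fit access prepared beforehand.

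A reader might go further and infer that week-16 visits fall before the 16-week course is complete. The documents do not support this, because the labels point to a count from intervention start. A delay common to all conditions would not favour one over another either, and weeks 5 and 10 are not among the time points the SAP lists for Aim 2b. The unstated clock origin needs a clarifying sentence; it is not a demonstrated misalignment.

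**Conclusion.** The order of steps is as described, and it leaves open a loss that is easy to avoid. Pre-call losses can enter the intent-to-treat analysis without treatment having started. With outcome data they attenuate every component effect: at 10% never starting, from 0.67 to 0.60, with power at 36 per group going from 80% to 71%. Without post-baseline data they reduce precision only. These figures rest on the assumed rates, equal loss across conditions, no component effect in never-starters and an unchanged SD.

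This is a design improvement, not an error in the analysis. Intent-to-treat is sound, and one might read the point as a claim that the component comparison is biased between conditions; nothing in the documents shows that.

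**What to change.** Draw the assignment at the start of the initial coach call, once the participant has joined. Check first that baseline weight and the 28-day binge count are on record; section 8.0 already collects both before enrolment. Use a concealed, computer-generated list that releases the assignment only after attendance is confirmed, and open the assigned content then. Define that date as week 0, and state visit windows. Keep everyone randomised in the intent-to-treat analysis. Because assignment follows attendance, leaving out non-attenders cannot bias the component comparison. Report the number enrolled but not started as a pre-randomisation feasibility result, so the next trial can allow for it.

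The cost is a few sentences in Protocol section 8.0 and the SAP, plus a way to release the assignment during the call. The downside is that pre-call losses leave the randomised denominator, so the Aim 2a average of sessions completed would no longer count them; give that figure with and without them. People who attend the call and then do not use the app remain in the analysis.

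If the present order has to stay, define week 0, set a maximum interval from randomisation to the call, give never-starters a due date for outcome visits, report them by condition, and add a sensitivity analysis restricted to those who attended the call.
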